# Appendix 6 Schedule of Assessments – Part 3 (Myelofibrosis)

									٦	reatn	nent l	Phase	þ				Safety Follow- up Visit c	Follow -up Phase d
	Sorooninga						We	eks						Wks 13-52	Wks 13-52 Wks >52 ET			Q12W
Study Weeks	Screening a	1	2	3	4	5	6	7	8	9	10	11	12	(Q3W)	(Q3W)	E 1	after last dose	QIZW
Study Window	-28 days						3	:3 day	/S					±3 d	±3 d	+3 d	+7 d	±10 d
Concomitant medications (including transfusions) v	x	х	x	x	x	x	x	х	х	x	х	х	х	х	х	x	x	х
Adverse events		Х	Х	Х	Х	Х	Х	Х	Х	Х	Х	Х	х	х	х	х	х	х
Time-to-next treatment																	х	Х
Survival																	х	Х

#### Footnotes for Appendix 6 ACE-LY-005 Schedule of Study Activities - Part 3 (Myelofibrosis):

Anti-HBc=hepatitis B core antibody; anti-HBs=hepatitis B surface antibody; BID=twice per day; CR=complete remission; CT=computed tomography; d=days; ECG=electrocardiogram, ECOG=Eastern Cooperative Oncology Group, ET=early termination; F/U=follow-up; HBsAg=hepatitis B surface antigen; HBV=hepatitis B virus; Ig=immunoglobulin; IVIG =intravenous immunoglobulins; JAK=Janus kinase; MF=myelofibrosis; MPN-SAF TSS=Myeloproliferative Neoplasm Symptom Assessment Form Total Symptom Score; MRI=magnetic resonance imaging; PCR=polymerase chain reaction; CCL PCR PE=physical examination; PR=partial response; Q3W=every 3 weeks; Q4W=every 4 weeks; Q9W=every 9 weeks; Q12W=every 12 weeks; QM=every month

- a Screening tests should be performed within 28 days before the first administration of study drug, unless otherwise indicated.
- b Treatment with acalabrutinib may be continued until disease progression or an unacceptable drug-related toxicity occurs as defined in the protocol. Treatment with pembrolizumab may continue for 24 months (103 weeks) from first dose of pembrolizumab, provided subjects are tolerating the drug and not progressing. Treatment may be stopped earlier for confirmed CR as described in the protocol. Treatment with acalabrutinib can continue until the end of trial, defined as 48 months after the last subject is enrolled, for subjects who are tolerating therapy and not progressing.
- c A 30-day (+7 days) safety follow-up visit is required when subjects discontinue study drug.
- d Subjects who discontinue study therapy will continue on study until withdrawal of consent, loss to follow-up, death, or study termination by the sponsor.
- e The screening physical examination will include, at a minimum, the general appearance of the subject, height (screening only) and weight, and examination of the skin, eyes, ears, nose, throat, lungs, heart, abdomen, extremities, musculoskeletal system, lymphatic system, and nervous system. As part of tumor assessment, Physical examinations, including presence and degree of splenomegaly and hepatomegaly (where appropriate) by palpation, are done thereafter.
- f Vital signs (blood pressure, pulse, and temperature) will be assessed after the subject has rested in the sitting position.
- g Subjects should be in supine position and resting for  $\geq 10$  minutes before study-related ECGs.
- h Women of childbearing potential must have a negative urine or serum pregnancy testing within 72 hours prior to receiving the first dose of study medication. If the urine test is positive or cannot be confirmed as negative, a serum pregnancy test is required.
- i Hematology includes complete blood count with peripheral blood smear and differential, and platelet and reticulocyte counts. Week 1 hematology does not need to be repeated if screening hematology was done within 7 days.
- j Serum chemistry: albumin, alkaline phosphatase, alanine transaminase, aspartate aminotransferase, bicarbonate, blood urea nitrogen, bone-specific alkaline phosphatase, calcium, chloride, creatinine, c-terminal telopeptide, glucose, lactate dehydrogenase, magnesium, phosphate, potassium, sodium, total bilirubin, total protein, and uric acid. Week 1 serum chemistry does not need to be repeated if screening chemistry was within 7 days.
- k Thyroid panel: total triiodothyronine, free thyroxine, and thyroid stimulating hormone. Week 1 thyroid panel does not need to be repeated if screening thyroid panel was within 7 days. Thyroid function tests will be performed once weekly for the first 8 weeks, followed by a Week 10 visit and then every 6 weeks thereafter until the 6-month timepoint. Thyroid testing may be discontinued at 6 months if 1) testing that was performed at 6 months was normal and 2) testing that was

performed 6 weeks prior to the 6-month timepoint was normal (for a total of 2 consecutive normal test results). Otherwise, thyroid testing will continue beyond the 6-month timepoint as scheduled until 2 consecutive normal test results.

- Urinalysis: pH, ketones, specific gravity, bilirubin, N-terminal telopeptide, protein, blood, and glucose.
- CC
- n Serum immunoglobulin: IgG, IgM, IgA.
- Molecular disease markers to be done at baseline and repeated as clinically indicated (at the investigator's discretion) to assess molecular response (see Section 4.2)
- p (Footnote not applicable for Part 3)
  - The indicated samples at this timepoint must be drawn predose.

#### r CCI

- t Subjects with MF will receive a run-in of 6 weeks of acalabrutinib alone. Subjects who are demonstrating a clinically meaningful response, in the opinion of the investigator, may continue on acalabrutinib monotherapy; those who are not will receive combination therapy thereafter.
- u MPN-SAF TSS will be assessed at the end of Week 6 (±7 days), end of Week 15 (±7 days), end of Week 24 (±7 days), every 9 weeks (±10 days) through Week 52, and every 12 weeks (±14 days) thereafter, or more frequently at investigator discretion.
- v Document all concomitant medications and procedures from within 21 days before the start of study drug administration through 30 days after the last dose of study drug. For subjects with MF, record all transfusions of blood products (e.g., red blood cells or platelets) within 12 weeks before the first study dose and throughout the study period.
- A pretreatment MRI or CT scan to measure spleen volume is required within 30 days of the first dose; this baseline MRI/CT scan must be done at least 2 weeks after the last dose of any JAK inhibitors. MRI is the preferred modality; the same modality (either MRI or CT) should be used for all timepoints for a given subject. On-treatment MRIs or CT scans will be done for spleen measurements at the end of Week 6 (±7 days), end of Week 15 (±7 days), end of Week 24 (±7 days), every 9 weeks (±10 days) through Week 52, and every 12 weeks (±14 days) thereafter, or more frequently at investigator discretion.
- x This peripheral blood sample will be collected if treatment termination is due to disease progression.
- y This urine or serum pregnancy test is to be performed on Cycle 1 Day 1 (- 3 days).
- z Hepatitis serology must include HBsAg, anti-HBs, anti-HBc, and hepatitis C antibody. Subjects who are receiving prophylactic IVIG and have positive HBsAg or anti-HBc must have negative hepatitis B DNA to be eligible. In addition, any subjects testing positive for any hepatitis serology, must have PCR testing (see exclusion criterion #30).
- aa Subjects who are anti-HBc positive (or have a known history of HBV) should be monitored every 3 months with a quantitative PCR test for HBV DNA and this testing is recommended to continue until 12 months after last dose of study drug(s). Any subject with a rising viral load (above lower limit of detection) should discontinue study drug(s) and have antiviral therapy instituted and a consultation with a physician with expertise in managing hepatitis B.

#### Appendix 7 Actions Required in Cases of Increases in Liver Biochemistry and Evaluation of Hy's Law

#### INTRODUCTION

This Appendix describes the process to be followed in order to identify and appropriately report potential Hy's law (PHL) cases and Hy's law (HL) cases. It is not intended to be a comprehensive guide to the management of elevated liver biochemistries.

During the course of the study the investigator will remain vigilant for increases in liver biochemistry. The investigator is responsible for determining whether a subject meets PHL criteria at any point during the study. All sources of laboratory data are appropriate for the determination of PHL and HL events; this includes samples taken at scheduled study visits and other visits, including central and all local laboratory evaluations, even if collected outside of the study visits (e.g., PHL criteria could be met by an elevated ALT from a central laboratory and/or elevated total bilirubin from a local laboratory). The investigator will also review adverse event (AE) data (e.g., for AEs that may indicate elevations in liver biochemistry) for possible PHL events.

The investigator participates with the sponsor in the review and assessment of cases meeting PHL criteria to agree whether HL criteria are met. HL criteria are met if there is no alternative explanation for the elevations in liver biochemistry other than drug induced liver injury (DILI) caused by the investigational medicinal product (IMP). The investigator is responsible for recording data pertaining to PHL/HL cases and for reporting AEs and SAEs according to the outcome of the review and assessment in line with standard safety reporting processes.

#### DEFINITIONS

#### Potential Hy's Law

AST or ALT  $\geq$ 3× ULN together with total bilirubin  $\geq$ 2× ULN at any point during the study after the start of study drug, irrespective of an increase in alkaline phosphatase.

#### Hy's Law

AST or ALT  $\geq$ 3× ULN together with total bilirubin  $\geq$ 2× ULN, where no other reason other than the IMP can be found to explain the combination of increases (e.g., elevated alkaline phosphatase indicating cholestasis, viral hepatitis, or another drug).

For PHL and HL, the elevation in transaminases must precede or be coincident with (i.e., on the same day) the elevation in total bilirubin, but there is no specified timeframe within which the elevations in transaminases and total bilirubin must occur.

#### IDENTIFICATION OF POTENTIAL HY'S LAW CASES

Laboratory data must be comprehensively reviewed by the investigator for each subject to identify laboratory values meeting the following criteria:

- ALT ≥3× ULN
- AST ≥3× ULN
- Total bilirubin ≥2× ULN

When the identification criteria are met from central or local laboratory results, the investigator will perform the following:

- Notify the sponsor representative/medical monitor by telephone and report the PHL case as an SAE of Potential Hy's law: seriousness criteria "important medical event" and causality assessment "yes/related" or in accordance with the clinical study protocol as appropriate.
- Request a repeat of the test (new blood draw) without delay
- Complete the appropriate unscheduled laboratory electronic Case Report Form (eCRF) module(s)
- Perform follow-up on subsequent laboratory results according to the guidance provided in the clinical study protocol, as applicable

## **REVIEW AND ASSESSMENT OF POTENTIAL HY'S LAW CASES**

The instructions in this section should be followed by the investigator for all cases where PHL criteria are met.

As soon as possible after the biochemistry abnormality is initially detected, the study medical monitor and the investigator will review available data to agree whether there is an alternative explanation for meeting PHL criteria other than DILI caused by the IMP and to ensure that timely analysis and reporting to health authorities within 15 calendar days from the date PHL criteria were met.

Where there is an agreed alternative explanation for the ALT or AST and total bilirubin elevations, a determination of whether the alternative explanation is an AE will be made and, subsequently, whether the AE meets the criteria for an SAE:

• If the alternative explanation is **not** an AE, record the alternative explanation on the appropriate eCRF

 If the alternative explanation is an AE/SAE, update the previously submitted PHL SAE and AE eCRFs accordingly with the new information (reassessing event term; causality, and seriousness criteria) following the sponsor's standard processes

If it is agreed that there is **no** explanation that would explain the ALT or AST and total bilirubin elevations other than the IMP, then:

- Send updated SAE (report term "Hy's law") according to the sponsor's standard processes:
  - The "Medically Important" serious criterion should be used if no other serious criteria apply.
  - Because there is no alternative explanation for the HL case, a causality assessment of "related" should be assigned.

If there is an unavoidable delay of over 15 calendar days in obtaining the information necessary to assess whether or not the case meets the criteria for HL, then it is assumed that there is no alternative explanation until an informed decision can be made:

- Provide any further update to the previously submitted SAE of PHL (report term now "Hy's law case"), ensuring causality assessment is related to IMP and seriousness criteria are medically important, according to clinical study protocol process.
- Continue follow-up and review according to the agreed plan. After the necessary
  supplementary information is obtained, repeat the review and assessment to determine
  whether HL criteria are still met. Update the previously submitted PHL SAE report following
  the clinical study protocol process, according to the outcome of the review.

## ACTIONS REQUIRED FOR REPEAT EPISODES OF POTENTIAL HY'S LAW

This section is applicable when a subject meets PHL criteria while receiving study treatment and has already met PHL criteria at a previous on-study treatment visit. The requirement to conduct follow-up, review, and assessment of a repeat occurrence(s) of PHL is based on the nature of the alternative cause identified for the previous occurrence.

The investigator should determine the cause for the previous occurrence of PHL and answer the following question:

Was the alternative cause for the previous occurrence of PHL determined to be the disease under study (e.g., chronic or progressing malignant disease, severe infection, or liver disease)?

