# 1.4.2.1 Safety of Acalabrutinib in Combination with Pembrolizumab for Subjects with B-Cell Malignancies (ACE-LY-005)

Study ACE-LY-005 is a Phase 1b/2, multicenter, open-label proof-of-concept study in subjects with B-cell malignancies. Safety data from 161 subjects are available as of the data cutoff date of 03 September 2017. Median exposure was 3.4 months (range 0.2 to 30.2 months).

All 161 subjects (100.0%) experienced at least 1 AE of any grade. The most frequently reported AEs were diarrhea (44.1%), headache (35.4%), fatigue (33.5%), cough (26.7%), nausea (26.7%), decreased appetite (24.8%), and vomiting (22.4%).

Nine subjects (5.6%) had Grade 5 (fatal) events, including 2 subjects with Grade 5 sepsis and 3 subjects with Grade 5 respiratory failure. One subject with DLBCL had Grade 5 neutropenic sepsis, which was considered by the investigator to be related to acalabrutinib. Two other subjects had Grade 5 events of respiratory failure and sepsis which were considered by the investigator to be related to pembrolizumab.

SAEs were reported for 73 subjects (45.3%). The most commonly reported SAEs were sepsis (5 subjects [3.1%]) and lung infection and AST increased (4 subjects [2.5%] each). Five subjects had SAEs reported by the investigator as related to only acalabrutinib of lymphoma, tumor flare, neutropenic sepsis (fatal event described above), nausea, and syncope.

Fifteen subjects had SAEs that were attributed to both acalabrutinib and pembrolizumab treatment. Of these 15 subjects, 1 subject experienced multiple related events of mental status change, pyrexia, lactic acidosis, and AST increased (Grade 3). Other SAEs related to both acalabrutinib and pembrolizumab were hypotension, dehydration, septic shock, systemic inflammatory response syndrome, ALT increased, Herpes zoster, lymphadenitis, cytokine release syndrome, lymphocyte count decreased, platelet count decreased, pancreatitis, pneumonitis, lymphoma, gastrointestinal hemorrhage, retroperitoneal mass, anemia, hyponatremia, upper gastrointestinal hemorrhage, enteritis, and neck pain.

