## 2.0 STUDY OBJECTIVES

## 2.1 PRIMARY OBJECTIVE

To characterize the safety profile of acalabrutinib and pembrolizumab in subjects with hematologic malignancies.

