## 3.8.1 Dose Modifications for Acalabrutinib

After the DLT review is cleared, the actions in Table 2 should be followed for the following toxicities:

- Grade 4 neutropenia (<500/µL) for >7 days (neutrophil growth factors are permitted per American Society of Clinical Oncology [ASCO] guidelines [Smith 2015] and use must be recorded on the case report form [CRF]).
- Grade 3 thrombocytopenia in presence of significant bleeding.
- Grade 4 thrombocytopenia.
- Grade 3 or 4 nausea, vomiting, or diarrhea, if persistent despite optimal antiemetic and/or anti-diarrheal therapy.
- Any other Grade 4 toxicity or unmanageable Grade 3 toxicity.

 Table 2
 Drug Discontinuation Actions for Acalabrutinib

Occurrence	Action
1 st - 2 nd	Hold acalabrutinib until recovery to Grade ≤1 or baseline; may restart at original dose level
3 rd	Hold acalabrutinib until recovery to Grade ≤1 or baseline; restart at one dose level lower (100 mg QD)
4 th	Discontinue acalabrutinib

If acalabrutinib is reduced for apparent treatment-related toxicity, the dose need not be re-escalated, even if there is minimal or no toxicity with the reduced dose. However, if the subject tolerates a reduced dose of acalabrutinib for  $\geq$ 28 days then the dose may be increased to the next higher dose level, at the discretion of the investigator. Such

re-escalation may be particularly warranted if further evaluation reveals that the AE that led to the dose reduction was not treatment-related. However, the maximum dose of acalabrutinib is 100 mg BID for this protocol.

Treatment with acalabrutinib should be withheld for any unmanageable, potentially study drug-related toxicity that is Grade  $\geq$ 3 in severity. Any other clinically important events where dose delays may be considered appropriate by the Investigator must be discussed with the medical monitor. Study drug may be withheld for a maximum of 28 consecutive days from expected dose due to toxicity. Study treatment should be discontinued in the event of a toxicity lasting >28 days, unless reviewed and approved by the medical monitor.

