#### Appendix 3 Adverse Event Assessment of Causality

Is there a reasonable possibility that the event may have been caused by study drugs?

No\_\_\_\_Yes\_\_\_

The descriptions provided below will help guide the principal investigator in making the decision to choose either "No" or "Yes":

**No=**There is no reasonable possibility that the event may have been caused by study drugs. The adverse event:

- May be judged to be due to extraneous causes such as disease or environment or toxic factors
- May be judged to be due to the subject's clinical state or other therapy being administered
- Is not biologically plausible
- Does not reappear or worsen when study drug is re-administered
- Does not follow a temporal sequence from administration of study drug

**Yes=**There is a reasonable possibility that the event may have been caused by study drugs. The adverse event:

- Follows a temporal sequence from administration of study drug
- Is a known response to the study drug based on clinical or nonclinical data
- Could not be explained by the known characteristics of the subject's clinical state, environmental or toxic factors, or other therapy administered to the subject
- Disappears or decreases upon cessation or reduction of dose of study drug
- Reappears or worsens when study drug is re-administered

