#### If the answer is Yes:

Determine whether there has been a significant change in the subject's condition compared with the previous occurrence of PHL. Note: A "significant" change in the subject's condition refers to a clinically relevant change in any of the individual liver biochemistry parameters (ALT, AST, or total bilirubin) in isolation or in combination or a clinically relevant change in associated symptoms. The determination of whether there has been a significant change will be at the discretion of the investigator; this may be in consultation with the study medical monitor if there is any uncertainty.

- If there is no significant change, no action is required.
- If there is a significant change, follow the process described in "Potential Hy's Law Criteria Met" in this Appendix for reporting PHL as an SAE.

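### Appendix 7 lets a repeat potential Hy's law episode skip the PHL SAE report and Hy's law review, because it counts severe infection and liver disease as the disease under study

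*Protocol*

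**What the plan says.** Protocol Appendix 7 defines PHL as AST or ALT at least 3x ULN with total bilirubin at least 2x ULN, whatever the alkaline phosphatase. Its identification section asks for a PHL case to be reported as an SAE, with related as the stated causality (or as the protocol provides), and for a prompt repeat blood draw. Its review section applies to every case that meets PHL criteria.

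A later section covers a subject on treatment who "has already met PHL criteria at a previous on-study treatment visit". The investigator is asked whether the previous episode was caused by "the disease under study (e.g., chronic or progressing malignant disease, severe infection, or liver disease". If no, the new episode is reported as a PHL SAE. If yes, the instruction is: "Determine whether there has been a significant change in the subject's condition compared with the previous occurrence of PHL". That decision is left to the investigator, and consulting the medical monitor is optional. Then: "If there is no significant change, no action is required".

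Three other places bear on this:

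- Section 2.1 states the primary objective: "To characterize the safety profile of acalabrutinib and pembrolizumab in subjects with hematologic malignancies".
- Appendix 3 lists, among the features that support a causal link: "Reappears or worsens when study drug is re-administered".
- Section 6.2.6 makes AST or ALT at least 3x ULN with bilirubin at least 2x ULN and alkaline phosphatase below 2x ULN an event of clinical interest (ECI). It is reportable within 24 hours whether or not it is related.

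**The concern.** An exemption for a known, stable background cause is reasonable. This one has two faults.

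First, the gate is too wide. Severe infection and liver disease are not the disease under study. Sections 3.3.1 and 3.3.2 admit subjects with hematologic malignancies and exclude active hepatitis B or C, bilirubin above 1.5x ULN and AST or ALT above 3x ULN. PHL-level values are therefore not an expected baseline state, and an infection on study is an acute event.

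Second, the comparator is the previous episode, with no regard to recovery in between. Recurrence after re-administration is the finding most able to overturn an earlier attribution to infection, yet a recurrence of the same size is no change on this comparison.

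At stake is the classification of serious liver events in a trial whose primary objective is safety. Section 3.10.4 warns that transaminase elevations may be more frequent and more severe with the combination than with either drug alone. SAP Section 9.7.1 tabulates serious and drug-related serious treatment-emergent AEs, so a repeat episode not entered as an SAE is absent from those tables.

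**Working it through.** The documents give no figure to reproduce; the check sets the passages side by side.

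**1. Can a restart happen after a liver event?** Yes, within limits. Table 2 in Section 3.8.1 says of first and second toxicities that the subject "may restart at original dose level". The hepatotoxicity text after it allows acalabrutinib to be considered once liver tests recover from a Grade 3 event, and after Grade 4 only following discussion with the medical monitor. Section 3.8.3 allows pembrolizumab to be reconsidered after a Grade 2 hepatic event but not after Grade 3 or 4.

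**2. Follow one subject through Appendix 7.**
- Episode 1: ALT 3x ULN and bilirubin 2x ULN during an infection. It is reported as a PHL SAE. Investigator and monitor agree on infection as the explanation, and the SAE is updated in term and causality.
- Drug is held, values recover, drug is restarted.
- Episode 2: ALT 3x ULN and bilirubin 2x ULN again. Change from episode 1: 3 − 3 = 0 and 2 − 2 = 0 (multiples of ULN). If the investigator keeps infection as the cause of episode 1 and sees no relevant change in symptoms, the outcome is no action.

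Because episode 1 has been re-attributed, episode 2 is the one that would have carried the drug-related signal.

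**3. What still applies to episode 2?**

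| Route | ALP <2x ULN | ALP ≥2x ULN |
|---|---|---|
| PHL SAE, related by default (Appendix 7) | Waived by the repeat-episode rule | Waived by the repeat-episode rule |
| Hy's law review (Appendix 7) | Required by the review section, waived by the repeat-episode rule | Same conflict |
| ECI within 24 hours (Section 6.2.6) | Required | Not triggered |
| AE report (Sections 6.1.1, 6.2.1) | If judged clinically significant | If judged clinically significant |

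**4. Does the ECI route replace what is waived?** Only in part. It carries no SAE status, no default causality and no repeat draw. Its footnote sends assessment and follow-up back to Appendix 7, where the waiver sits. It also requires the low alkaline phosphatase to be present at the same time, whereas Appendix 7 sets no time limit between the transaminase and bilirubin rises.

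**5. Cross-references.** Both branches of the repeat-episode rule point to a process called *Potential Hy's Law Criteria Met*. No heading in the supplied Appendix 7 has that title; *Identification of Potential Hy's Law Cases* is evidently meant.

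**6. Context for size.** Section 1.4.2.1 reports, among 161 subjects, sepsis SAEs in 5 (5/161 = 3.1%) and lung infection SAEs in 4 (4/161 = 2.5%). ALT and AST increases led to study drug discontinuation in 8 and 7 subjects. None of these counts PHL, repeat PHL or rechallenge. As an illustration only, exact two-sided 95% limits are:
- 0/161: upper limit 1 − 0.025^(1/161) = 2.27%.
- 1/161 = 0.62%: lower limit 1 − 0.975^(1/161) = 0.02%; upper limit 3.41%.

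This shows how one case moves a rare-event estimate in 161 subjects. It does not estimate how often the rule would bite.

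**The case against.** A reader might infer that such a recurrence need not be reported at all, with no SAE, no repeat draw and no review. The documents do not support that. Section 6.2.6 has no exemption for repeat episodes, and Section 6.2.1 requires all AEs and SAEs to be reported regardless of causality. Section 6.1.1 makes clinically significant laboratory abnormalities AEs and gives the withholding of study drug as an example of significance. Section 6.1.2 lets the investigator call any event serious on medical judgement. Appendix 7's review section, read alone, still covers the episode. Section 3.8.3 calls for liver-test monitoring of pembrolizumab-related hepatic events, and SAP Section 9.7.2 tabulates worst laboratory grade whatever was put on SAE forms.

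Nor does the text force the outcome. The investigator must establish the cause of the previous episode, and a recurrence without infection could change that answer to no. A relevant change in symptoms also counts as significant. The discontinuation counts are not evidence of rechallenge, and the infection counts contain no liver data.

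All of this stands, and it confines the point to the PHL SAE, its default causality and the Hy's law review. It does not remove the point. The ECI route leads back to Appendix 7 for assessment and misses PHL episodes with alkaline phosphatase at 2x ULN or above. A worst-grade shift table shows one worst value per parameter, so a second rise to the same grade would not appear as a second event.

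**Conclusion.** The point holds in this limited form. For a repeat PHL episode resembling one attributed to the disease under study, Appendix 7 waives the PHL SAE report and Hy's law review, and it wrongly puts severe infection and liver disease under that heading. The waiver conflicts with the review section's coverage of all PHL cases and fits poorly with Appendix 3, which counts reappearance on re-administration as support for causality. Reporting as an ECI remains when alkaline phosphatase is below 2x ULN; above that, it depends on the investigator's judgement.

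The size is unknown. The conclusion assumes that a restart occurs, that the earlier attribution is kept, and that the investigator sees no significant change; the text permits each but requires none. Any bias would be toward fewer drug-related serious liver events, but the documents do not show that it has occurred. The change is worth making because it is cheap and protects the primary objective.

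**What to change.** All changes concern reporting; no dosing or treatment rule is touched.

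1. In *Actions Required for Repeat Episodes of Potential Hy's Law*, delete severe infection and liver disease, so that the examples are limited to the subject's hematologic malignancy.
2. Under *If the answer is Yes*, allow no action only for one continuing episode, for example where values have not fallen below the PHL thresholds since the previous report. Send a new PHL after recovery, or after re-administration of either study drug, through the identification and review sections. The exact definition of a continuing episode is for the sponsor to settle.
3. Reconcile the repeat-episode rule with the review section and Section 6.2.6, stating that no action under Appendix 7 leaves the ECI and AE duties in force and saying what applies when alkaline phosphatase is 2x ULN or above.
4. Point both cross-references to *Identification of Potential Hy's Law Cases*.

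The cost is a few sentences in Appendix 7, plus a few more SAE forms and case reviews for repeat episodes.
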